8. SAFETY

No inferential statistics will be performed on safety data.

All case report form (CRF) data will be listed by subject and chronologically by assessment time points. This will include rechecks, unscheduled assessments, and early termination.

Applicable continuous variables will be summarized using n, arithmetic mean, SD, minimum, median, and maximum. Data from subjects who received the placebo treatment will be pooled across cohorts.

The level of precision will be presented as follows: minimum/maximum in the same precision as in the database, mean/median in one more precision level than minimum/maximum, SD in one more precision level than mean/median, and n will be presented as an integer.

Where individual data points are missing because of dropouts or other reasons, the data will be summarized based on reduced denominators.

8.1 Subject Discontinuation

Subjects will be summarized by number of subjects dosed, completed, and discontinued the study with discontinuation reasons by treatment (pooled placebo and xisomab 3G3 dose levels), pooled active, and overall. Any screen failure data will be listed.

8.2 Demographics

Descriptive statistics will be calculated for continuous variables (age, weight, height, and body mass index) by treatment (pooled placebo and xisomab 3G3 dose levels), pooled active, and overall. Age will be derived from date of birth to date of first dosing and reported as an integer. Any screen failure data will be listed.

Frequency counts will be provided for categorical variables (race, ethnicity, and sex) by treatment (pooled placebo and xisomab 3G3 dose levels) and overall.

8.3 Adverse Events and Injection Site Reaction

All adverse events (AEs) occurring during this clinical trial will be coded using the Medical Dictionary for Regulatory Activities (MedDRA®), Version 20.0.

All AEs captured in the database will be listed in by-subject data listings including verbatim term, coded term, treatment, severity, relationship to study drug, and action; however, only treatment-emergent AEs (TEAEs) will be summarized.

A TEAE is defined as an AE that is starting or worsening at the start time of study drug administration or after. Each TEAE will be attributed to a treatment based on the onset date and time of the AE.

If an AE increases in severity, that AE will be given a resolution date and time and a new record will be initiated with the new severity. If the severity of an AE remains the same or decreases, the AE will be kept open through to resolution.

If the onset time of an AE is missing and the onset date is the same as the treatment dosing date or after the treatment dosing date, then the AE will be considered treatment emergent. If the onset date of an AE is missing, then the AE will be considered treatment emergent.

TEAEs will be tabulated by System Organ Class (SOC) and Preferred Term. Summary tables will include number of subjects reporting the AE and as percent of number of subjects dosed by treatment (pool placebo and xisomab 3G3 dose levels) and pooled active (xisomab 3G3 doses pooled). The number of AEs will be tabulated in a similar manner. Tables which tabulate the number of TEAEs by severity and relationship to study treatment will also be included.

Injection site reaction will be assessed and any abnormal finding will be reported as an adverse event.

Serious adverse events (SAEs), if present, will also be listed. Applicable narratives will be included in the CSR.

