### **9.2 Study Endpoints**

The primary endpoints of the study will be the number and severity of TEAEs following single doses of xisomab 3G3 and placebo.

The secondary endpoints are as follows:

1. The following PK parameters of free xisomab 3G3 in plasma following single IV dose, will be calculated, as appropriate: AUC0-t, AUC0-inf, AUC%extrap, Cmax, Tmax, Kel, T1/2, MRT, CL, and Vss.
2. aPTT values will be listed and presented graphically. PD parameters for aPTT following single IV doses of xisomab 3G3 may be calculated if deemed appropriate.

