#### **10.2.4 Follow-up Visit**

Subjects for whom aPTT value reaches  $\pm 10\%$  of the baseline value or within the normal range by Day 29 will return to the CRU for the FU visit on Day 36 to perform scheduled follow-up procedures and to determine if any AE has occurred since the last study visit.

Subjects for whom aPTT did not reach  $\pm 10\%$  of the baseline value or within the normal range on Day 29, will return every 7 days ( $\pm 2$  days) until aPTT reach  $\pm 10\%$  of the baseline value or within the normal range and for the FU visit (i.e., follow-up procedures and AE evaluation) 7 days ( $\pm 2$  days) after it was reached. If aPTT values remain elevated past Day 29, an additional ADA sample collection will occur at the FU visit.

Subjects who terminate the study early will be asked to continue aPTT monitoring as scheduled in the Study Events Flow Chart ([Section 6](#)) until it reaches  $\pm 10\%$  of the baseline value or within the normal range. They will return to the CRU approximately 7 days ( $\pm 2$  days) after aPTT reaches  $\pm 10\%$  of the baseline value or within normal range for the FU visit to perform scheduled follow-up procedures, and to determine if any AE has occurred since the last study visit. They will also be asked to return on Days 15 and 29 to collect the ADA samples.

The follow-up procedures are listed in the Study Events Flow Chart (see [Section 6](#)).

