#### **11.1.9.2 Monitoring**

Subjects will be monitored throughout confinement for adverse reactions to the study drug and/or procedures. Subjects will be asked how they are feeling once per day during confinement and at each return/follow-up visit.

AEs (whether serious or non-serious) and clinically significant abnormal laboratory test value(s) will be evaluated by the PI or designee and treated and/or followed up until the symptoms or value(s) return to normal, or acceptable levels, as judged by the PI or designee.

Treatment of SAEs will be performed by a licensed medical provider, either at Celerion or at a nearby hospital emergency room. Where appropriate, medical test(s) and/or examination(s) will be performed to document resolution of event(s). Outcome may be classified as resolved, improved, unchanged, worse, fatal, or unknown (lost to follow up).

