Subjects for whom aPTT value reaches \pm 10% of the baseline value or within the normal range by Day 29 will return to the CRU for the follow-up visit on Day 36 to perform scheduled follow-up procedures and to determine if any adverse event has occurred since the last study visit.

Subjects for whom aPTT did not reach $\pm 10\%$ of the baseline value or within the normal range on Day 29, will return every 7 days (± 2 days) until aPTT reaches $\pm 10\%$ of the baseline value or within the normal range and for the follow-up visit.

Subjects who terminate the study early will be asked to continue aPTT monitoring until it reaches $\pm 10\%$ of the baseline value or within the normal range. They will return to the CRU approximately 7 days (± 2 days) after aPTT reaches $\pm 10\%$ of the baseline value or within normal range for the follow up (FU) visit to perform scheduled follow-up procedures and to determine if any AE has occurred since the last study visit. They will also be asked to return on Days 15 and 29 to collect the anti-drug antibody (ADA) samples.

ADA sample collection will be performed on Days 15 and 29 for all subjects. If aPTT values remain elevated past Day 29, an additional ADA sample collection will occur at the follow-up visit.

Dose escalation to the next dose level (i.e., next cohort) will not take place until the safety review committee (SRC) has determined that adequate safety and tolerability of xisomab 3G3 from the current and previous cohorts has been demonstrated to permit proceeding to the next cohort.

The total planned duration of subject participation is up to 63 days from screening to follow-up, if aPTT value returns within \pm 10% of the baseline value or the normal range by Day 29. This participation could be prolonged if aPTT values did not reach \pm 10% of the baseline value or within the normal range by Day 29.

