14.3 Safety Data Summary Tables

14.3.1 Displays of Adverse Events

Table 14.3.1.1 Treatment-Emergent Adverse Event Frequency by Treatment

- Number of Subjects Reporting the Event (% of Subject Dosed) (Safety Population)

- Table 14.3.1.2 Treatment-Emergent Adverse Event Frequency by Treatment

 Number of Adverse Events (% of Total Adverse Events)

 (Safety Population)
- Table 14.3.1.3 Treatment-Emergent Adverse Event Frequency by
 Treatment, Severity, and Relationship to Drug Number of
 Adverse Events (Safety Population)

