			Median	X.XX	X.XX	X.XX	X.XX	X.XX	X.XX	X.XX	X.XX
			Minimum	X.XX	X.XX	X.XX	X.XX	X.XX	X.XX	X.XX	X.XX
			Maximum	X.XX	X.XX	X.XX	X.XX	X.XX	X.XX	X.XX	X.XX
	1	0.5	N	X.XX	X.XX	x.xx	X.XX	X.XX	X.XX	X.XX	X.XX
	_	0.5	Mean	X.XX	X.XX	X.XX	X.XX	X.XX	X.XX	X.XX	X.XX
			SD	X.XX	X.XX	X.XX	X.XX	X.XX	X.XX	X.XX	X.XX
			Median	X.XX	X.XX	X.XX	X.XX	X.XX	X.XX	X.XX	X.XX
			Minimum	X.XX	X.XX	X.XX	X.XX	X.XX	X.XX	X.XX	X.XX
			Maximum	X.XX	X.XX	X.XX	X.XX	X.XX	X.XX	X.XX	X.XX

Notes for Generating the Actual Table:

- Per study design, an additional column for treatment D will be added
- aPTT values will be presented with the same level of precision as received from the clinical laboratory database

- Summary statistics presentation with respect to the precision of the clinical laboratory data: n = integer; Mean and Median +1; SD and SEM +2, Min and Max +0, CV% to 1 decimal
- PD Time points are: predose and 0.083, 0.25, 0.5, 1, 3, 8, 24, 72, 120, 168, 216, 336, 504, and 672 hours postdose (additional time points might be added depending on the conduct of the study)

Add the following to the footnote:

Treatment A: Single IV Infusion of 0.1 mg/kg xisomab 3G3 Treatment B: Single IV Infusion of 0.5 mg/kg xisomab 3G3 Treatment C: Single IV Infusion of 2 mg/kg xisomab 3G3 Treatment D: Single IV Infusion of 5 mg/kg xisomab 3G3 Treatment P: Single IV Infusion of Placebo (Pooled)

Table 14.3.1.1 Treatment-Emergent Adverse Event Frequency by Treatment - Number of Subjects Reporting the Event (% of Subjects Dosed) (Safety Population)

	Treatment							
Adverse Event*	А	В	C	D	Pooled Placebo Pooled Active			
- Number of Subjects Dosed	XX (XXX%) XX (XXX%)	XX (XXX%) X	X (XXX%)) XX (XXX%) XX (XXX%)			
Number of Subjects With TEAEs	X (X%	X (XX%)	X (X%)	X (XX%)) X (XX%) X (XX%)			
Number of Subjects Without TEAEs	XX (XX%) XX (XX%)	XX (XX%) X	X (XX%)) XX (XX%) XX (XX%)			
Eye disorders	X (X%) X (X%)	X (X%)	X (X%)) X (X%) X (X%)			
Vision blurred	X (X%) X (X%)	X (X%)	X (X%)) X (X%) X (X%)			
Gastrointestinal disorders	X (X%) X (X%)	X (X%)	X (X%)) X (X%) X (X%)			
Dyspepsia	X (X%) X (X%)	X (X%)	X (X%)) X (X%) X (X%)			
Nausea	X (X%) X (X%)	X (X%)	X (X%)) X (X%) X (X%)			
Musculoskeletal and connective tissue disorders	X (X%) X (X%)	X (X%)	X (X%)) X (X%) X (X%)			
Back pain	X (X%) X (X%)	X (X%)	X (X%)) X (X%) X (X%)			
Muscle cramps	X (X%) X (X%)	X (X%)	X (X%)) X (X%) X (X%)			
Musculoskeletal pain	X (X%) X (X%)	X (X%)	X (X%)) X (X%) X (X%)			

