		SD	X.XX	X.XX	X.XX	X.XX	X.XX			
		Minimum	XX	XX	XX	XX	XX			
		Median	X.X	X.X	X.X	X.X	X.X			
		Maximum	XX	XX	XX	XX	XX			

Programmer note: Time points are Screen, Baseline, Day 1 Hour 0.25, Day 8, Day 29, and Follow-up.

Note: Treatment A: < >
 Treatment B: < >
 Treatment C: < >
 Treatment D: < >

Baseline is the last predose measurement.

Change From Baseline Table 14.3.5.16 will resemble 14.3.5.15

Page 1 of X

Table 14.3.5.15 12-Lead Electrocardiogram Summary (Safety Population)

			Treatment							
Measurement (units) Time	Point	Statistic	А	А В		D	Pooled Placebo			
Testname (unit) Scre	en	n	X	Х	X	Х	X			
		Mean	X.X	X.X	X.X	Х.Х	X.X			
		SD	X.XX	X.XX	X.XX	X.XX	X.XX			
		Minimum	XX	XX	XX	XX	XX			
		Median	X.X	X.X	X.X	X.X	X.X			
		Maximum	XX	XX	XX	XX	XX			
Base	line	n	X	Х	X	X	Х			
		Mean	X.X	X.X	X.X	X.X	X.X			
		SD	X.XX	X.XX	X.XX	X.XX	X.XX			
		Minimum	XX	XX	XX	XX	XX			
		Median	X.X	X.X	X.X	X.X	X.X			
		Maximum	XX	XX	XX	XX	XX			
Day	1 Hour 0.25	n	X	X	X	X	X			
		Mean	X.X	X.X	X.X	X.X	X.X			
		SD	X.XX	X.XX	X.XX	X.XX	X.XX			
		Minimum	XX	XX	XX	XX	XX			
		Median	X.X	X . X	X.X	X.X	X.X			
		Maximum	XX	XX	XX	XX	XX			

Programmer note: Time points are Screen, Baseline, Day 1 Hour 0.25, Day 8, Day 29, and Follow-up.

Note: Treatment A: < >
Treatment B: < >
Treatment C: < >
Treatment D: < >

Baseline is the last predose measurement.

Table 14.3.5.17 ADA Detection Summary by Collection Time and Treatment (Safety Population)

				Treatm	Treatment					
Time Point	Assay Type		- - A			D	Pooled Placeb			
Predose	Screening	Negative Positive	X X	X X	X X	X X	X X			
	Confirmatory	Negative Positive	X X	X X	X X	X X	X X			
Day 15	Screening	-	Х	X	X	Х	X			
	Confirmatory	Positive Negative Positive	X X X	X X X	X X X	X X X	X X X			
Day 29	Screening		X	X	X	X	X			
	Confirmatory	Positive Negative Positive	X X X	X X X	X X X	X X X	X X X			
Follow-up	Screening	Negative	X	X	X	X	X			
	Confirmatory	_	X X	X X	X X	X	X X			
Overall*	Screening	Positive Negative	X	X X	X X	X	X X			
	Confirmatory	Positive Negative		X X	X X	X X	X X			
		Positive	X	X	X	X	X			

Note: Follow-up ADA detection sample only collected if Follow-up visit occurred after Day 36.

*For overall counts, if the response of a subject is positive at least once, the subject will be counted as positive; otherwise, the subject will be considered negative.

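### TEAEs have no end day, while follow-up runs past Day 36 only if aPTT is unrecovered on Day 29; no planned summary by treatment gives follow-up length or TEAEs over a common window

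*SAP*

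**What the plan says.** Protocol 9.2 defines the primary endpoint: "The primary endpoints of the study will be the number and severity of TEAEs following single doses of xisomab 3G3 and placebo". SAP 8.3 gives the counting rule: "A TEAE is defined as an AE that is starting or worsening at the start time of study drug administration or after". It states no last day.

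Follow-up length depends on aPTT. Under SAP 3, a subject whose aPTT is back within 10% of baseline or "within the normal range by Day 29 will return to the CRU for the follow-up visit on Day 36". Under Protocol 10.2.4, a subject not recovered on Day 29 returns every 7 days (±2) until recovery and has the follow-up visit 7 days (±2) after that. AEs are sought throughout (Protocol 11.1.9.2): "Subjects will be asked how they are feeling once per day during confinement and at each return/follow-up visit". Each extra aPTT visit is therefore also an extra AE enquiry.

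The planned TEAE tables (SAP 10.2, item 14.3.1, and in-text Table 12-1) give subjects with an event, as in "Number of Subjects Reporting the Event (% of Subject Dosed) (Safety Population", then event counts, then event counts by severity and relationship. None has a day limit or a time denominator. The disposition summary (SAP 8.1) gives dosed, completed, discontinued and reason, but not length of follow-up.

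Both documents provide for extension elsewhere. Protocol 10.2.4 says: "If aPTT values remain elevated past Day 29, an additional ADA sample collection will occur at the FU visit". The shell of SAP Table 14.3.5.17 carries the note "Follow-up ADA detection sample only collected if Follow-up visit occurred after Day 36".

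**The concern.** The trigger for longer observation is the drug's own pharmacodynamic marker. Protocol 11.1.9.1 calls prolonged aPTT an expected pharmacological effect. Protocol 8.2 and 8.3.3 report that its duration rose with dose in animals. Placebo subjects enter with aPTT in the normal range (Protocol 10.3.2) and have no drug-related reason to be extended.

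If extension happens, active subjects, most plausibly at 5 mg/kg, are questioned about AEs for longer than placebo subjects, as a consequence of treatment. Their number and percentage with TEAEs could then be somewhat higher with no difference in AE rate. With four subjects at each dose and five on pooled placebo, one additional subject moves a dose arm by 25 percentage points. The planned TEAE tables would not separate longer observation from a higher rate.

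**Working it through.** **1. The plan's own duration.** Screening up to 28 days (Protocol 10.2.1), plus Day 1 to Day 36 = 35 days, gives 28 + 35 = 63 days. This matches Protocol 10.1.2, which attaches the figure to recovery by Day 29.

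**2. Length of an extended follow-up.** With k weekly visits after Day 29 until recovery, the nominal last visit is Day 29 + 7k + 7.
- k = 1: Day 43, or 42 days after dosing; 42/35 = 1.20. With the ±2-day windows the ratio runs from (28+5+5)/35 = 1.09 to (28+9+9)/35 = 1.31.
- Each further week adds 0.20. No fixed last day is set.

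**3. Is extension plausible?** Protocol 8.3.3 reports prolongation in monkeys until 336 h at 2 mg/kg and 672 h at 10 mg/kg. Observation stopped at 28 days, so 672 h is a minimum. Assume that the durations carry over to humans and rise linearly with log dose. Let E2 be the end of effect at 2 mg/kg.
- Slope per dose doubling ≥ (672 − E2)/log2(5). End at 5 mg/kg ≥ E2 + log2(2.5) × slope.
- E2 = 336 h: slope ≥ 336/2.322 = 144.7 h; end ≥ 336 + 1.322 × 144.7 = 527 h (Day 23.0).
- E2 = 504 h (assumed, if the effect outlasted the reported time): end ≥ 600 h (Day 26.0).
- Slope needed to reach the 672 h visit = (672 − E2)/1.322: 254 h for E2 = 336, 127 h for E2 = 504. If elimination is first order, one dose doubling adds about one half-life. The longest half-life in Protocol 8.3.2 is 248 h.

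On these figures extension at 5 mg/kg is borderline, and less likely at lower doses. They also overstate it. They track prolongation in monkeys, whereas a subject still above baseline but within 23-32 seconds (Protocol Appendix 1) counts as recovered in this trial.

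**4. Effect on the TEAE tables if extension occurs.** The documents give no AE rate. Assume 0.5 AE per subject in 35 days, no drug effect and one extra week. Let f be the share of AEs that occur early and do not recur at a constant rate: f = 0 (constant rate) or f = 0.8.
- Ratio of expected events per extended subject: r = 1 + (1 − f) × 0.20 = 1.20 or 1.04.
- P(at least one TEAE) = 1 − exp(−0.5r): 39.3% at 35 days; 45.1% (f = 0) or 40.5% (f = 0.8) at 42 days.
- Difference d = 0.0577 or 0.0120: the chance that a given extended subject has a first TEAE only in the extra week.

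| 5 mg/kg arm (n = 4) | One subject extended | All four extended |
|---|---|---|
| Expected TEAEs (2.00 without extension) | 2.02-2.10 | 2.08-2.40 |
| Chance that the count of subjects with a TEAE rises by at least one, 1 − (1 − d)^m for m extended | 1.2-5.8% | 4.7-21.2% |

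With 0.25 to 2 AEs per subject, the chance with all four extended is 3-24%. Pooled active (16 subjects) moves from 39.3% to 39.6-40.8% with all four extended.

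**5. What the planned outputs show.**
- AE listing 16.2.7.1.1 gives treatment, onset date and time, and an elapsed-time column for each event.
- The concentration tables by treatment (14.2.1.1 to 14.2.1.5) can show extension, since "additional time points might be added depending on the conduct of the study" and PK sampling continues until aPTT recovers.
- The Follow-up row of ADA Table 14.3.5.17 shows how many per arm were sampled after Day 36.

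None of these gives TEAE incidence to a common day, or follow-up length, by treatment.

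**The case against.** **Extension may never happen.** This stands. If every subject recovers by Day 29, completers share one 35-day window and the issue disappears. A reader might infer from the dose-dependent duration that the 5 mg/kg arm will be observed longer and that its TEAE comparison is biased. The documents do not support that: the extrapolated minimum falls before Day 29, and return to the normal range also ends the extension.

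**The information is already visible.** Largely true. A reader might infer that extended follow-up is hidden, or can only be rebuilt from several listings. That also goes too far. With 21 planned subjects, late-onset events can be read by treatment from the single AE listing, and the PK and ADA tables can show who was extended. What remains is that by-subject displays are not a by-treatment summary of the primary endpoint.

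**Counting every event is a legitimate safety choice.** Agreed. Drug effect persists during an extension, and those events belong in the main tables. Prolonged aPTT is itself not an AE, so the trigger does not create TEAEs directly. The split by severity and relationship helps interpretation but does not equalise the observation period.

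**The SAP lets extra analyses be described in the study report.** True (SAP 1), but a window chosen after the data are seen is weaker than one fixed beforehand.

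**Conclusion.** The point holds as a conditional gap in presentation. The counting rule has no end day, the observation period depends on the drug's marker, and no planned summary by treatment shows follow-up length or TEAEs over a common window.

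If extension occurs, the effect is modest: about a 1-6% chance that the 5 mg/kg count of subjects with a TEAE rises by at least one if one subject is extended, and 5-21% if all four are. This rests on an assumed 0.5 AE per subject, one extra week, and either a constant rate or 80% of AEs occurring early. A longer extension would raise it.

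No test is affected, because SAP 8 plans no inference on safety. Escalation is not affected either, because the safety review committee works from blinded data through Day 29 (Protocol 10.4.1.4). This is a low-cost improvement worth considering, not an error that undermines the trial.

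**What to change.** In SAP 8.3, leave all existing TEAE tables as they are. Add that, if any subject enters extended follow-up because aPTT had not recovered by Day 29, the report will also give, by treatment:

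- (a) the subject-count, event-count and severity summaries restricted to TEAEs with onset through Study Day 36 (dosing date + 35 days);
- (b) days from dosing to last visit, including early terminators.

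SAP 8.3 already treats an AE with missing onset date as treatment emergent. In line with that, count it in the Day 36 summary and footnote it. If no subject is extended, say so in one sentence and omit the extra tables. Tying the trigger to aPTT recovery means that a recovered subject whose Day 36 visit slips by a day does not set it off.

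Cost: a paragraph of SAP text, a date filter on the AE data and, only if extension occurs, one extra set of descriptive tables. No AE leaves the main tables, and no visit or clinical procedure changes.

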#### **11.1.9.3 Reporting**

All AEs that occurred during this clinical trial will be recorded. AEs will be coded using the most current MedDRA® available at Celerion.

The PI or designee will review each event and assess its relationship to drug treatment (likely, probably, possibly, unlikely or unrelated). Each sign or symptom reported will be graded on the FDA (Center for Biologics Evaluation and Research) toxicity grading scale for healthy volunteers 4-point severity scale (Grade 1, 2, 3 and 4). The date and time of onset, time relationship to drug dosing, duration, and outcome of each event will be noted.

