2.2 Endpoints

The primary endpoints of the study will be the number and severity of treatmentemergent adverse events (TEAEs) following single doses of xisomab 3G3 and placebo. Other safety endpoints include clinical laboratories, vital signs, electrocardiograms, physical examinations, and immunogenicity.

- The following PK parameters of free xisomab 3G3 in plasma following single IV dose, will be calculated, as appropriate: AUC0-t, AUC0-inf, AUC%extrap, Cmax, Tmax, Kel, T½, MRT, CL, and Vss.
- aPTT values will be listed with descriptive statistics and presented graphically.

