Appendix 16.2.4.3 Medical History (Safety Population)

Page 1 of X

						Dat	e		
	Subject	Any		System Organ Class/	-				
Cohort			System Reviewed	Preferred Term*	Category S	Start	End	Ongoing?	Condition or Event
X	1	No							
	2	Yes	XXXXXXXXXXXXX	XXXXXXXX/XXXXXXX	Medical Y	YYYY		YES	< >

<Note date can be YYYY, MONYYYY, or DDMONYYYY based on individual subject data.>

Note: *Medical history events are classified according to MedDRA Version 20.0.

Program: /CAXXXXX/sas prg/stsas/standardlis/cdash lis mh.sas 27NOV2015 18:35

Celerion, Clinical Study Report No. CA19214

Page 1 of X

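### SAP 8.3 classes an AE with a missing onset date, or a missing onset time on the dosing day, as treatment-emergent even when its recorded stop precedes the infusion

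*SAP*

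**What the plan says.** The primary endpoint rests on the treatment-emergent flag. Protocol 9.2 states: "The primary endpoints of the study will be the number and severity of TEAEs following single doses of xisomab 3G3 and placebo". SAP 2.2 repeats it. SAP 8.3 adds that all AEs are listed but "only treatment-emergent AEs (TEAEs) will be summarized".

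SAP 8.3 defines the flag by timing: "A TEAE is defined as an AE that is starting or worsening at the start time of study drug administration or after". It then gives two defaults for incomplete onset data:

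- Missing time. The sentence that begins "If the onset time of an AE is missing and the onset date is the same as the treatment dosing date" makes the event treatment-emergent. It does the same for later dates.
- Missing date. "If the onset date of an AE is missing, then the AE will be considered treatment emergent".

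Neither default refers to the stop date or time, and no other section of the protocol or SAP adds an exception.

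Predose events can be in the AE data. Protocol 11.1.9.3 says "All AEs that occurred during this clinical trial will be recorded", and the listing shell in SAP Appendix 16.2.7.1.1 has a treatment-emergence column with a sample entry of No.

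The SAP has no rule for partial AE onset dates. Partial dates are mentioned only in the medical history shell, Appendix 16.2.4.3: "Note date can be YYYY, MONYYYY, or DDMONYYYY based on individual subject data".

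**The concern.** A default that counts undated events as treatment-emergent is sensible in a first-in-human trial when nothing else is known. Here it also applies when something else is known. If the record shows that the event was over before the infusion began, its timing relative to dosing is settled whatever its onset. The rule still puts it in the treatment-emergent tables.

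The primary result is a set of counts in very small groups, so a single wrongly flagged event is visible in a percentage column. The information that would prevent this is part of the plan: SAP 8.3 itself refers to a resolution date and time for an AE record, and Protocol 11.1.9.3 asks for duration and outcome.

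**Working it through.** The documents give no figure to reproduce. The check sets the definition beside the defaults, case by case, and then sizes one event.

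**Step 1: definition against default (SAP 8.3)**

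- Case A: onset date missing, recorded stop before the infusion. An event that ended before the infusion began before it and could not worsen after it. Definition: not treatment-emergent. Default: treatment-emergent. They conflict.
- Case B: onset dated on the dosing day, onset time missing, recorded stop time before the infusion. The same reasoning gives the same conflict.
- Case C: onset date missing, stop after the infusion started or not recorded. The definition cannot be applied. The default decides, and there is no conflict.
- Case D: partial onset date whose known part precedes dosing. No rule is stated. The definition excludes the event unless it worsens after dosing. A programmer who takes a missing date to include an incomplete one would flag it. The text does not say which.

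Could a record that stopped before the infusion hide later worsening? No. SAP 8.3 closes a record when severity increases and opens a new one, so worsening after dosing would have its own record.

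**Step 2: size of one event**

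Group sizes are from SAP 5.

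- Each dose level: 4 active subjects. 1/4 = 25 percentage points.
- Pooled placebo: 2 + 1 + 1 + 1 = 5. 1/5 = 20 points.
- Pooled active: 4 × 4 = 16. 1/16 = 6.25 points.

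These are ceilings for the number of subjects with any treatment-emergent AE (Table 14.3.1.1). They apply only if the event is that subject's sole treatment-emergent AE. The event counts in Tables 14.3.1.2 and 14.3.1.3 rise by one in every instance.

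**Step 3: how often**

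The documents give no expected number of AEs with missing onset, nor of those with a predose stop. The number may be zero. No sample size, power or error rate is involved: Protocol 12.1.1 gives no statistical basis for the sample size, and SAP 8 plans no inference on safety data.

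**The case against.** The case for leaving the text alone has several parts.

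- **The default is conservative.** The definition needs an onset, and the disputed sentences say what to do without one. This stands for Case C. It does not stand for Cases A and B, where the stop settles the question.
- **The record is unlikely.** Protocol 11.1.9.3 has date and time of onset noted for each event. Subjects are housed from Day -1 until after the 24-hour procedures (Protocol 10.1.1) and are asked daily how they feel (11.1.9.2). Protocol 13.3 plans a full quality control check and edit checks for missing and inconsistent data. This stands, and it keeps the point small. It does not make the rule correct when such a record survives; the SAP evidently thought missing onsets possible enough to need a rule.
- **The effect on interpretation is limited.** Safety analysis is descriptive, every AE is listed individually, and Table 14.3.1.3 splits events by relationship to drug, where an unreasonable time sequence supports an unrelated rating. The escalation criteria in Protocol 10.4.1.4 refer to SAEs, emergency room visits and graded AEs, not to the treatment-emergent flag. All of this stands.

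A reader might infer two stronger points that the documents do not support.

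- **That an AE with a partial onset date known to precede dosing is counted.** The SAP does not say so. It is silent, and its definition points the other way. This is a gap, not a stated error.
- **That bruising or bleeding from predose bleeding-time tests or blood draws would be misread as a drug effect because of this rule.** The defect needs a recorded stop before the infusion. A bruise from that morning would usually outlast the infusion, and with no onset time it would stay treatment-emergent under the proposed wording too.

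**Conclusion.** The point holds in a narrow form. As written, SAP 8.3 flags an AE with a missing onset date, or with a missing onset time on the dosing day, as treatment-emergent even if its recorded stop precedes the infusion. Such an event cannot meet the SAP's own definition, but it enters the primary endpoint summaries.

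The effect is confined to records of that kind, possibly none. The ceilings per event are 25, 20 and 6.25 percentage points for a dose level, pooled placebo and pooled active. They assume the planned group sizes with all planned subjects dosed. Partial onset dates are a separate, unaddressed case in which two programmers could reach opposite results. The point is minor: worth correcting because it is nearly free, not because it threatens the trial's conclusions.

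**What to change.** Add one sentence to SAP 8.3, before unblinding, to this effect: *An AE with a missing onset date, or with a missing onset time on the dosing day, is treatment-emergent unless its recorded stop date/time is before the start of infusion; an AE with a partial onset date whose known part precedes dosing is not treatment-emergent unless it worsens after dosing.*

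Undetermined events stay treatment-emergent. That includes an event with no recorded stop, and one that stopped on the dosing day with no stop time, because neither is shown to have ended before the infusion.

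The cost is that sentence and the matching condition in the derivation of the flag. No table shell has to change: excluded events still appear in the AE listing, marked as not treatment-emergent. Footnotes in the summary tables to mark events flagged by default would be a matter of preference.
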